### 12.3.2 Prior/Concomitant Medications

Prior/concomitant medications will be coded by World Health Organization Drug Dictionary 2018Mar01 DDE + HD and will be summarized by Anatomic Therapeutic Classification (ATC) class and preferred name. The analysis will be performed using the ITT population.

The numbers and percentages of subjects using each medication will be displayed for within double-blind treatment period and throughout the study. Subjects taking more than one medication in the same ATC class or preferred name will be counted once for the number of subjects taking that preferred name.

## 12.4 Demographic and Baseline Characteristics

Demographic and baseline characteristics (sex, ethnicity, race, age, age group ( $\geq 2$  to  $<12$ ,  $\geq 12$  to  $<18$  or  $\geq 18$ ), weight [kg], height [cm], body mass index [BMI; kg/m^2]) will be summarized by treatment using descriptive statistics for subjects in ITT Analysis Set. Qualitative variables (age group, sex, ethnicity, race, wart characterization category, and wart location) will be summarized using frequencies while quantitative variables (age, weight, height, BMI, wart size, and number of warts) will be summarized using mean, SD, median, minimum, and maximum. Demographic and baseline data will also be listed for subjects for the ITT Analysis Set.

General Medical/Surgical History will be coded by MedDRA version 19.1 or later, as applicable at time of analysis and will be presented by subject listing.

Cutaneous Common Wart History will be listed by subject.

## 12.5 Efficacy Analyses

The primary and secondary efficacy analyses are planned analyses and the tertiary analyses are exploratory only in order to gain insight regarding the pharmacodynamic nature of the treatment response.

Wart assessments are conducted at Screening, Baseline, Week 2, Week 4, Week 6/EOT, Week 12, Week 18/End of Post-treatment Efficacy Evaluation, and Week 30 Follow up (for the subset of subjects). Wart characterization categories (solitary and cluster/splitting/satellite), the total number of warts, and the location (hands: dorsal, periungual, and palmar; foot: dorsal, limbs: arm and leg; and trunk) will be tabulated for the baseline visit for the ITT analysis set, using descriptive statistics.

The changes from baseline in total wart sizes (mm) will be summarized by group and by visit. Clinical clearance of a wart, as determined by the PI or an appropriately qualified Sub-I, should be recorded with a size of 0 mm in the CRF.

Wart assessment data will be listed for all subjects.

New common warts that appear after the Baseline visit will be identified, characterized and location recorded/mapped only, but not treated in this study. Any new common warts will be summarized in ITT analysis set for descriptive purpose and listed by subject.

Clinical Photography information collected in the CRF will be listed.

### 12.5.1 Primary Variable

The Primary efficacy analyses will be performed on the ITT analysis set to test the difference in the proportion of subjects with complete clearance of all treated warts (i.e., Baseline Treated warts) between the active and vehicle at Week 18 /End of Post-treatment Efficacy Evaluation.

- Primary efficacy endpoint
  - Proportion of subjects with complete clearance of all treated warts at Week 18 End of Post-treatment Efficacy Evaluation.

Proportion of subjects with complete clearance of all treated warts is defined as the percentage of the number of subjects who have all baseline treated warts as “clinical clearance” at Week 18 out of the total subjects in the ITT Analysis Set.

Statistical comparisons of proportions of subjects with all treated warts cleared will be made using Cochran-Mantel-Haenszel (CMH) test for treatment stratified by age group ( $\geq 2$  to  $< 12$ ,  $\geq 12$  to  $< 18$  or  $\geq 18$ ) and investigative site at  $\alpha = 0.05$ . The number and percentage of subjects achieving complete clearance of all treated warts (i.e., Baseline Treated warts) will be presented by group. The 95% confidence interval will be based on the asymptotic Wald CI and will be constructed for the difference of the proportions of 2 treatments. P-value from CMH test will be presented.

The Breslow-Day chi-square test for homogeneity of the odds ratios across strata will be used to check the assumption. If the assumption test fails, the nature of the difference may be further explored, e.g. subgroup analysis by site and by age group may be explored.

The above primary efficacy analysis will be repeated on the PP analysis set as supportive.

## 12.5.2 Methods for Handling Dropouts and Missing Data

The frequency and percentage of missing values for each variable will be reported.

The primary method of dealing with missing data will be fully conditional specification (FCS) multiple imputations (MI; also called multiple imputation by chained equation [MICE]).

FCS MI relaxes the assumption of joint multivariate normality of all variables. FCS MI specifies the multivariate imputation model on a variable-by-variable basis on a set of conditional densities, one for each incomplete variable. Buuren, et al (2011) and Lee and Carlin (2012) provide results from simulation studies that suggest that FCS MI generally yields estimates that are unbiased with proper standard errors and provide appropriate coverage when data are missing at random (MAR).

For the multiple imputations, twenty sets of imputed data will be generated. These will be imputed using SAS Proc MI as shown below.

```
Proc MI NIMPUTE=20 SEED=861879112 ROUND=....111111  
      MINIMUM=....1000000 MAXIMUM=....666666;  
      class treat site sex agegrp;  
      var treat site sex agegrp w0 w2 w4 w6 w12 w18;  
      fcs logistic(treat) logistic(site) logistic(sex) logistic(agegrp) reg(w0) reg(w2)  
      reg(w4) reg(w6) reg(w12) reg(w18);  
      run;
```

Where:

treat = study treatment (CLS006,  
Vehicle) site = investigative site  
sex = sex (male, female)  
agegrp = age group ( $\geq 2$  to  $< 12$ ,  $\geq 12$  to  $< 18$  or  
 $\geq 18$ )  
w0 = number of warts at baseline (total number to be treated during the study)  
w2 = number of remaining treated warts at Week 2  
w4 = number of remaining treated warts at Week 4  
w6 = number of remaining treated warts at Week 6  
w12 = number of remaining treated warts at Week 12  
w18 = number of remaining treated warts at Week 18

Note: Variable names may differ from those used in the actual programs, but the methodology will be the same.

If an imputed value is not within the appropriate range for each variable in the model after the default of 100 tries, the SAS Proc MI option MINMAXITER may be increased in order to impute appropriate values.

The PROC FREQ procedure will be used to perform the *Cochran–Mantel–Haenszel test* and

---

will take the output dataset created from the MI procedure described above.

```
*** Obtain Mantel-Haenszel estimates ***;  
PROC FREQ data=imputed;  
  table site*agegrp*treat*response / cmh;  
  ODS OUTPUT cmh=cmh;  
  by _imputation_;  
RUN;
```

The chi-square distribution is highly skewed for smaller degrees of freedom, and thus obtaining a combined result of the CMH test from multiply-imputed data requires a transformation that would normalize the CMH statistic that have a mean = 0 and unity variance. Given that the chi-square distribution for the CMH test has 1 degree of freedom, a square root transformation will be used for this purpose.

```
*** Square root transformation of the CMH statistic resulting in a normalized variate ***;  
DATA cmh_std;  
  SET cmh(WHERE=(AltHypothesis="General Association"));  
  cmh_value_std= value**.5;  
  cmh_sterr_std = 1.0;  
RUN;
```

The multiple results from the CMH will be combined using PROC MIANALYZE

```
*** Combine transformed estimates;  
PROC MIANALYZE DATA=cmh_std;  
  ODS OUTPUT PARAMETERESTIMATES=mian_cmh_std;  
  MODELEFFECTS cmh_value_std;  
  STDERR cmh_sterr_std;  
RUN;
```

A one-sided p-value for the combined CMH will be obtained from the normal test produced by PROC MIANALYZE on the transformed statistic. This will be done using the SAS Code below.

```
*** Compute one-sided p-value;  
DATA mian_cmh_std_p;  
  SET mian_cmh_std;  
  IF tValue > 0 THEN Probt_upper = Probt/2;  
  
  ELSE Probt_upper = 1-Probt/2;  
RUN;
```

Last Observation Carried Forward (LOCF) and Baseline Observation Carried Forward (BOCF) will be used as sensitivity analyses.

LOCF sensitivity analysis will be performed on the primary endpoint, where values from a

---

subject's prior non-missing observation (including baseline and post-baseline) will be imputed for any missing post baseline visit for which there is a prior non-missing value.

BCOF sensitivity analysis will also be performed on the primary endpoint, where the baseline observation is treated as the final response from the subject if it is missing.

In general, data will not be imputed for safety analysis.

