## 6.1 Sample Size Considerations

The sample size estimates for the current study are based upon the rates of clearance of warts in the previous Phase 2 study [REDACTED]. This was a randomized, double blind, vehicle controlled, Phase II study in 80 subjects who were treated with topical [REDACTED], furosemide, [REDACTED], or vehicle for 42 days daily with an 8-week follow-up period. For the furosemide treatment group, the proportion of subjects with all cleared warts was 0.1 (10%) versus 0 in the vehicle.

The difference in the proportion of subjects with all treated warts cleared (complete clearance) at the Week 18/End of Post-Treatment Efficacy Evaluation period (EOS) is the primary endpoint of the current study. For conservative purposes, assuming 10% and 2% complete clearance rates in the furosemide and vehicle treated groups, respectively, 200 subjects randomized per treatment group will provide for 92% power at a two-sided  $\alpha$  of 0.05 to detect a difference between active and vehicle treated groups.

With the inclusion of an additional 80 subjects in the  $\geq 2$  to  $< 12$  cohort, the total sample size of 480 will provide 96% power with the assumption unchanged.

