## 6.2 Randomization

Subjects that meet all inclusion and exclusion criteria will be randomized to one of two treatment groups in a 1:1 ratio for each study center according to a predetermined computer-generated randomization code.

Subjects will be randomized to treatment using an Interactive Web Response System (IWRS). The randomization scheme will include age stratum at 3 levels ( $\geq 2$  to  $< 12$ ,  $\geq 12$  to  $< 18$  or  $\geq 18$ ) and investigative site.

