### **12.5.3 Multiplicity**

The primary and secondary endpoints will be tested at a two-sided 0.05 level of significance sequentially in the order presented in sections 7.1 and 7.2. However, to control type-1 error, the statistical testing will stop if non-significant superiority of active to vehicle ( $p>0.025$  one-sided) is observed.

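### Twenty imputations leave avoidable seed noise in the complete-clearance tests; the risk to the verdict is small, and a larger pre-specified number nearly removes it.

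*SAP*

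**What the plan says.** SAP 12.5.2 makes multiple imputation the primary method for missing data: "For the multiple imputations, twenty sets of imputed data will be generated". The code line reads "Proc MI NIMPUTE=20 SEED=861879112". Protocol 7.7.5 gives the same number and seed.

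The same SAP section then takes the square root of the CMH statistic from each completed data set, assigns it a standard error of 1, pools with PROC MIANALYZE and derives a one-sided p-value. The end of SAP 12.5.5 extends imputation to the same endpoint at other visits, that is, complete clearance at Weeks 12 and 6. Imputation is not stated for the cleared-wart ratio (Wilcoxon test) or for wart size (ANCOVA).

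SAP 12.5.3 says "The primary and secondary endpoints will be tested at a two-sided 0.05 level of significance sequentially", and "the statistical testing will stop if non-significant superiority of active to vehicle" is observed, with one-sided p above 0.025 as the criterion.

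Neither document gives an expected missing-data rate, a Monte Carlo error check or a rule for raising the number of imputations. The missing-data sensitivity analyses are LOCF and BOCF, which vary the missing-data assumption and say nothing about simulation noise.

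**The concern.** Multiple imputation estimates its pooled result from a finite number of random draws, so part of the reported Z belongs to the seed and not to the data. The endpoint is sparse. At the planning rates about 24 clearances are expected on active (0.10 x 240) and 5 on vehicle (0.02 x 240 = 4.8), so a few imputed clearances move the statistic visibly.

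The result then meets a hard cut with a stop rule. Three tests in the sequence carry this noise: complete clearance at Weeks 18, 12 and 6. A failure at the Week 12 clearance test, for example, would end four later tests: Week 6 clearance, the Week 12 and Week 6 ratios, and Week 18 wart size. If the true answer lay close to the cut, the seed could settle it. That is avoidable in a study meant to support a marketing application.

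**Working it through.** **Inputs from the documents.** M = 20 imputations and one seed (SAP 12.5.2, protocol 7.7.5). Standard error 1 for each square-rooted CMH statistic (SAP 12.5.2). One-sided cut of 0.025, that is Z = 1.96 (SAP 12.5.3). Planning rates of 10% and 2% with 240 per arm, allocated 1:1 (SAP 6.1 and 6.2).

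**Assumption.** The between-imputation variance B of Z is taken as 0.05 to 0.19. The fraction of missing information is B/(1+B), or 5% to 16%. In simulated trials with assumed wart counts, dropout and site pooling, 5% missing gave B of about 0.06-0.07, 10% about 0.10-0.12 and 15% about 0.15-0.20.

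**Step 1: the plan's own figure.** With pooled rate 0.06, the null standard error is sqrt(2 x 0.06 x 0.94/240) = 0.02168. The standard error under the alternative is sqrt((0.09 + 0.0196)/240) = 0.02137. Power is Phi((0.08 - 1.96 x 0.02168)/0.02137) = 96.0%. The same formula at 200 per arm gives 92.4%. Both agree with the stated 96% and 92%. The expected Z at design is 0.08/0.02168 = 3.69, or about 3.69/sqrt(1.05) = 3.60 after the information loss at B = 0.05.

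**Step 2: seed-only SD of the pooled Z.** With T = 1 + (1 + 1/M)B, two parts combine:

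- noise in the average: sqrt(B/M)/sqrt(T);
- noise from estimating B on the same M draws, at Z = 1.96: 1.96 x (1 + 1/M)/(2T) x B x sqrt(2/(M-1)).

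For M = 20:

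- B = 0.05: sqrt(0.0025)/sqrt(1.0525) = 0.049. The second part is 0.978 x 0.0162 = 0.016. Together 0.051.
- B = 0.19: sqrt(0.0095)/sqrt(1.1995) = 0.089. The second part is 0.858 x 0.0616 = 0.053. Together 0.103.

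**Step 3: chance of a changed verdict.** If the large-M Z is normal with mean E and SD 1, the chance that one run falls on the other side of the cut is about phi(1.96 - E) x SD x sqrt(2/pi), with sqrt(2/pi) = 0.798.

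- E = 3.6, B = 0.05: 0.104 x 0.051 x 0.798 = 0.4%.
- E = 3.0, B = 0.19: 0.232 x 0.103 x 0.798 = 1.9%.
- E = 1.96 (worst case), B = 0.19: 0.399 x 0.103 x 0.798 = 3.3%.

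**Step 4: results.** Direct simulation of the pooling step, with B re-estimated and the t reference distribution, agrees with these formulas:

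| B | M | Seed SD of Z | 95% seed range of p, true p = 0.025 | Changed verdict, E = 3.6 | E = 3.0 | E = 1.96 |
|---|---|---|---|---|---|---|
| 0.05 | 20 | 0.051 | 0.020-0.032 | 0.4% | 0.9% | 1.7% |
| 0.12 | 20 | 0.081 | 0.017-0.036 | 0.7% | 1.5% | 2.6% |
| 0.19 | 20 | 0.103 | 0.016-0.040 | 0.9% | 1.9% | 3.3% |
| 0.05 | 200 | 0.016 | 0.023-0.027 | 0.1% | 0.3% | 0.5% |
| 0.19 | 200 | 0.032 | 0.022-0.029 | 0.3% | 0.6% | 1.0% |
| 0.05 | 500 | 0.010 | 0.024-0.026 | 0.1% | 0.2% | 0.3% |
| 0.19 | 500 | 0.020 | 0.023-0.028 | 0.2% | 0.4% | 0.7% |

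**Cross-check on full simulated trials near the cut.** With 5% missing and a large-M p of 0.0206, 13% of seeds failed at M = 20, 1% at M = 100 and about none at M = 200. With 20% missing and a large-M p of 0.0312, 17% of seeds passed at M = 20, 4% at M = 100 and about none at M = 200.

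**The case against.** The strongest reply is that little is at stake, and most of it stands. At the design effect the primary test lies well beyond the cut. The plan runs one seed once, so what matters is the unconditional chance of a changed verdict, and that is about 1% to 3%. Rubin's (1 + 1/M) term already charges the analysis for using few imputations. The seed is written into both documents, so the result is reproducible and cannot be picked afterwards. Any p-value near a threshold is fragile for other reasons too.

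Two stronger readings are tempting, and the documents support neither:

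- A reader might take trials already selected to lie near the cut, run several seeds on each, and count any reversal. That gives an alarming proportion, but it answers a question the plan does not pose: there is one trial, one seed, and no ground for presuming a borderline result.
- A reader might infer that the Week 12 and Week 6 clearance tests are the most exposed because they lie closer to the cut. The planning rates in SAP 6.1 are for Week 18 only, and no effect is given for the earlier visits. Those tests are also reached only after the primary and the Week 18 ratio have passed. If dropout is cumulative, earlier visits have less to impute.

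What the reply does not answer is that the noise is avoidable almost for free, and that the remedy is available only in advance. Raising the number after a near miss would look data-driven.

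**Conclusion.** The point holds as a modest one about stability. With 20 imputations the seed contributes an SD of about 0.05 to 0.10 to the pooled Z. One run would disagree with a large-M analysis in about 0.4-2% of trials at an expected Z of 3.0 to 3.6, and in at most about 3% at any effect. Disagreements go in both directions. The effect is arbitrariness near the cut and a slight loss of power; the finite number of imputations does not inflate type I error.

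The size rests on the assumed B of 0.05 to 0.19, because the documents give no missing rate. Heavier missingness would widen it. At B = 0.25 the Step 2 formula gives sqrt(0.0995^2 + 0.0661^2) = 0.12, and the worst-case disagreement becomes 0.399 x 0.12 x 0.798 = 3.8%.

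**What to change.** Before unblinding, change `NIMPUTE=20` in SAP 12.5.2 to at least 200 (500 is also acceptable) and correct the sentence that gives the number. Keep the seed. Report the Monte Carlo error of the pooled Z with each imputed complete-clearance result.

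Because protocol 7.7.5 contains the same code, record the departure in SAP 4.1, which now lists no changes, or amend the protocol. Protocol 7.7.1 allows the SAP to set out deviations from the protocol's methods.

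At 200 imputations the seed SD falls to about 0.02-0.03 and the disagreement rate to 1% or less; 500 brings the SD to 0.01-0.02. The cost is slightly more computing and one documented change. Endpoint, alpha, sample size and test order are untouched.

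### The code for the primary p-value takes an unsigned square root of the CMH chi-square, so the one-sided superiority p-value is the same whichever arm is ahead

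*SAP*

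**What the plan says.** SAP 12.5.1 sets the primary test: "Statistical comparisons of proportions of subjects with all treated warts cleared will be made using Cochran-Mantel-Haenszel (CMH) test for treatment stratified by age group" and by investigative site, at alpha 0.05. SAP 12.5.2 settles how incomplete data enter it: "The primary method of dealing with missing data will be fully conditional specification (FCS) multiple imputations", and "For the multiple imputations, twenty sets of imputed data will be generated". The printed SAS code therefore produces the primary p-value. It does the following:

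- It runs the stratified CMH test in each imputed dataset and keeps the General Association statistic.
- It computes "cmh_value_std= value.5", that is, the chi-square to the power one half, and assigns a standard error of 1.0.
- It combines the 20 values in PROC MIANALYZE.
- It forms the one-sided p-value by "IF tValue > 0 THEN Probt_upper = Probt/2", with one minus that half as the ELSE branch.

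The stated reason for the root is the need for "a transformation that would normalize the CMH statistic that have a mean = 0 and unity variance".

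SAP 12.5.3 tests the primary and secondary endpoints in order at a two-sided 0.05 level, but "the statistical testing will stop if non-significant superiority of active to vehicle" is observed, defined as one-sided p above 0.025. Protocol 7.7.6.2 has the same rule.

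**The concern.** The General Association statistic for two arms and a binary response is a chi-square on 1 degree of freedom. It measures how far the arms differ and says nothing about which is better. Its positive root is |Z|, not Z. The ELSE branch shows that a directional p-value was intended, but no step in SAP 12.5.1 to 12.5.3 puts the direction back.

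This p-value decides the primary endpoint and whether the secondary endpoints may be tested. If it ignores direction, the written rule can record superiority of CLS006 when vehicle cleared more subjects. SAP 12.5.5 carries the CMH test and the multiple imputation over to complete clearance at Weeks 12 and 6, so the same gap recurs later in the sequence.

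**Working it through.** **Inputs from the documents.** 1:1 allocation and about 240 per arm; planning rates 10% and 2% (SAP 6.1); 20 imputations and standard error 1.0 (SAP 12.5.2); one-sided limit 0.025 (SAP 12.5.3).

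**The plan's own power figures.** Use the normal approximation with pooled null variance, mean rate 0.06, difference 0.08 and two-sided 0.05: power = Φ[(0.08 − 1.96 × √(2 × 0.06 × 0.94/n)) / √((0.10 × 0.90 + 0.02 × 0.98)/n)].

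- n = 200: (0.08 − 1.96 × 0.02375)/0.02341 = 1.43, power 92.4% (SAP: 92%).
- n = 240: (0.08 − 1.96 × 0.02168)/0.02137 = 1.76, power 96.0% (SAP: 96%).

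The sample size is not in question.

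**What the code computes.** With R the root from each imputation and B the variance of R between imputations, pooling gives t = mean(R)/√T, where T = 1 + (1 + 1/20)B. Every R is at least 0, so t is at least 0. The ELSE branch is reached only if every statistic is exactly 0, and then p = 0.5. The coded p can never exceed 0.5.

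**The stated justification.** Under the null, the unsigned root is half-normal, with mean √(2/π) = 0.798 and variance 1 − 2/π = 0.363. Mean 0 and variance 1 hold only for the signed root.

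**Worked tables.** One stratum, 240 per arm, no missing data. With a clearances on CLS006 and m in total, the expected number is m/2 and the variance is 240² × m × (480 − m)/(480² × 479). For 8 v 20: m = 28, expected 14, variance 7 × 452/479 = 6.605, chi-square 36/6.605 = 5.45, Z = −2.33.

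| Cleared, CLS006 v vehicle | Chi-square | Coded one-sided p | Signed one-sided p |
|---|---|---|---|
| 24 v 5 | 13.22 | 0.00014 | 0.00014 |
| 5 v 24 | 13.22 | 0.00014 | 0.9999 |
| 8 v 20 | 5.45 | 0.0098 | 0.990 |
| 5 v 14 | 4.43 | 0.018 | 0.982 |

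Mirror-image results get the same coded p. The last three rows all meet the 0.025 limit with vehicle ahead.

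**Simulation of the pooling rule.** 20,000 trials per setting, 240 per arm, 20 imputations, pooling as above with a t reference. Assumptions that are not in the documents: 12 equal strata, the common null rates, missingness of 0%, 10% or 20% (no dropout rate is given), and an arm-level imputation in place of the SAP's FCS model. Entries are the percentage of trials with p at or below 0.025, coded / signed.

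| True rates, CLS006 v vehicle | 0% missing | 10% missing | 20% missing |
|---|---|---|---|
| 2% v 2% | 4.5 / 2.2 | 5.0 / 2.6 | 5.5 / 2.7 |
| 6% v 6% | 4.8 / 2.4 | 4.9 / 2.5 | 5.0 / 2.6 |
| 10% v 10% | 4.6 / 2.4 | 5.2 / 2.5 | 5.3 / 2.6 |
| 10% v 2% | 97.6 / 97.6 | 96.3 / 96.3 | 93.7 / 93.7 |
| 2% v 6% | 62.7 / 0.0 | 58.3 / 0.0 | 53.4 / 0.0 |
| 2% v 10% | 98 / 0.0 | 96 / 0.0 | 94 / 0.0 |

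Monte Carlo error near 5% is about √(0.05 × 0.95/20,000) = 0.15 percentage points. In the equal-rate rows, about half of the coded passes have vehicle ahead.

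**The case against.** The code reading is not open to dispute; the practical harm is.

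SAP 12.5.1 tests a difference at alpha 0.05, SAP 12.5.3 also names a two-sided 0.05 level, and SAP 6.1 powers the trial on that basis. Without missing data, a coded p of 0.025 or less is exactly the ordinary two-sided CMH test at 0.05. The excess over 2.5% consists of results that favour vehicle. This stands: two-sided error is not grossly inflated, and what fails is the one-sided reading.

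SAP 12.5.1 also reports group percentages and a Wald interval for the difference, so a reader would probably notice the wrong direction. The Wilcoxon and ANCOVA steps in SAP 12.5.5 are two-sided too, so direction must be read from the estimates there in any case. This is fair on likelihood. But none of those outputs feeds the p-value or the stopping rule, and the SAP does not require the check.

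The 94% to 98% figures need true rates that reverse the planning assumption. They show what the rule does, not what is likely to happen. The strata, missingness and imputation model are assumed, but the sign error depends on none of them.

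**Conclusion.** The concern holds. As written, the one-sided p-value for the primary endpoint ignores direction and cannot exceed 0.5, so it does not test superiority of CLS006 over vehicle. This follows from the printed code alone.

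The size rests on the simulation assumptions listed above. The nominal one-sided 0.025 rule operates at about 0.05, with about half of the null passes favouring vehicle. The planned power and the result for a real CLS006 benefit are unaffected. A false claim of efficacy is unlikely to survive a look at the percentages, but a confirmatory rule should not rely on that. The code should be corrected before unblinding, because a change of sign made afterwards would be open to challenge.

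**What to change.** In SAP 12.5.2, give each root its direction before PROC MIANALYZE: multiply the square root of the chi-square by the sign of the sum over strata of observed minus expected clearances in the CLS006 arm. The sign of the log Mantel-Haenszel common odds ratio is equivalent, because in each stratum observed minus expected equals (ad − bc)/n. State the ordering of treatment and response levels, so that positive means CLS006 is better. Keep the standard error of 1 and the existing p-value step, which then works as intended. Restate the claim of mean 0 and unit variance so that it refers to the signed root.

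Apply the same code to complete clearance at Weeks 12 and 6. Add to SAP 12.5.3 that the estimate must favour CLS006 for testing to continue, which also covers the two-sided secondary tests.

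Pooling a stratified risk difference with its own standard error would also work and would give a matching interval, but it replaces the CMH test named in Protocol 7.7.6.1 and SAP 12.5.1. The signed root is the smaller change.

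The cost is a few lines of SAS, since the sign must be derived and merged by imputation, plus the SAP wording. It needs no new data and loses no power.
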